14.2. Dose Escalation

Prior to enrolling subsequent cohorts, the safety data in each prior cohort will be evaluated after 8 subjects have reached 2 months of treatment to assure there is no safety signal. Two months was selected as the time for the safety review because all of the clinically significant KD025-related AEs to date occurred within 36 days or less of starting dosing with KD025. As this is an open-label study, safety results will be continuously monitored. If $\geq 25\%$ of subjects in a cohort experience a CTCAE v4.03 Grade 2 liver toxicity or a CTCAE v4.03 Grade 3 (or higher) AE in the same organ or body system, or if $> 25\%$ of subjects in a cohort are discontinued for toxicity that persists for 14 days, then dose escalation to the next cohort will not occur, and all patients in that dose cohort will be dose reduced.

14.3. Missed Doses

Subjects should make every effort to take the study drug at the same scheduled time daily. In the event that the subject misses the planned dose of study drug, the following protocol should be followed:

For subjects receiving study drug on a QD dosing schedule:

- If less than 12 hours of time have elapsed after the scheduled dose, the drug should be taken. The subject should then resume the regular planned daily dosing schedule the following day.
- If more than 12 hours of time have elapsed after the scheduled dose, the drug should be skipped for that day. The subject should then resume the regular planned dosing schedule the following day.

For subjects receiving study drug on a BID dosing schedule:

- If less than 6 hours of time have elapsed after the morning scheduled dose, the drug should be taken. The subject should then resume the regular planned dosing that evening. If less than 6 hours of time have elapsed after the evening scheduled dose, the drug should be taken. The subject should then resume the regular planned dosing the following morning.

- If more than 6 hours of time have elapsed after the morning scheduled dose, the drug should be skipped and the subject should resume the regular planned dosing schedule that evening. If more than 6 hours of time have elapsed after the evening scheduled dose, the drug should be skipped and the subject should resume the regular planned dosing the following morning.

If the subject skips more than 7 consecutive days of drug, the subject should be discontinued from the study.

14.4. Dose Pause or Reduction of KD025

Exacerbation of any of the signs or symptoms of the disease will constitute a potential rationale for cessation of therapy. Any clinically significant toxicity will necessitate consideration of either a pause or cessation of therapy. Both laboratory and clinical data may constitute a reason to pause or cease therapy. Previous studies have indicated that reversible and modest liver toxicity may occur spontaneously after a few weeks of initiation of therapy.

- When treatment-related Grade 3 toxicities occur, drug administration will be halted until recovery to at least Grade 1, at which time study drug may be resumed at a reduced dose.
- When treatment-related Grade 2 toxicities, other than liver toxicities, occur, drug administration will be halted until recovery to at least Grade 1 at which time study drug administration may resume at the same dose.
- When greater than Grade 2 liver toxicities occur, drug administration will be halted until recovery to at least Grade 1 at which time study drug administration may resume at a reduced dose.

Pauses in therapy may not last more than 14 days; subjects requiring pauses of more than 14 days will be discontinued from the study. If treatment-related Grade 2 or treatment-related Grade 3 toxicities persist for 14 days, subjects will be discontinued from the study.

14.4.1 Dose Reduction Steps

Every effort should be made to keep the subject on the full dose of drug. When dose reduction is necessary (see [Section 14.4](#)), the drug should be decreased as shown in [Table 5](#) (for subjects on 100 mg capsules) and [Table 6](#) (for subjects on 200 mg tablets), until the event has resolved. Once a subject has the dose decreased, an increase is not allowed.

Table 5: Dose Reductions for Toxicity Related to Study Drug – 100 mg Capsule

Study Drug	Cohort	Starting Dose	Dose Reduction
KD025	Cohort 1	200 mg KD025 QD	100 mg KD025 QD
KD025	Cohort 2	200 mg KD025 BID	200 mg KD025 QD
KD025	Cohort 3	400 mg KD025 QD	200 mg KD025 QD

BID = twice daily; QD = once daily

No more than 1 dose reduction is permitted. Subjects who require more than 1 dose reduction will have study drug discontinued and enter the Follow-Up Period.

Table 6: Dose Reductions for Toxicity Related to Study Drug – 200 mg Tablet

Study Drug	Cohort	Starting Dose	Dose Reduction
KD025	Cohort 1	200 mg KD025 QD	200 mg KD025 QOD
KD025	Cohort 2	200 mg KD025 BID	200 mg KD025 QD
KD025	Cohort 3	400 mg KD025 QD	200 mg KD025 QD

BID = twice daily; QD = once daily; QOD = every other day

No more than 1 dose reduction is permitted. Subjects who require more than 1 dose reduction will have study drug discontinued and enter the Follow-Up Period.

14.5. Identity of Investigational Products

KD025 will be supplied by Kadmon Corporation.

14.6. Study Drug Packaging and Labeling

KD025 will be packaged and labeled by the sponsor. The label attached to each bottle will provide the following information:

- Description of contents (number and strength of capsules) and route of administration
- Directions for use
- Storage conditions
- Product identification code
- Lot Number identification
- Bottle number
- Name of protocol sponsor
- The statement, “Caution: New Drug – Limited by Federal Law to Investigational Use”
- The statement, “Keep out of the reach of children and pets.”

14.7. Dispensing of Study Drug and Dosing Compliance

Subjects will be dispensed study drug to self-administer while on an outpatient basis. Subjects will return to the clinic as outlined in the Study Assessments (Table 1), and will receive that day's dose of study drug while at the clinic.

The amount of study drug dispensed to the subject at the beginning of each dosing month should be sufficient to allow for 1 month of dosing with KD025.

The investigator (or designee) will be responsible for recording this information on the appropriate study drug inventory. This inventory will be maintained throughout the duration of the trial and will be periodically reviewed by a representative of the sponsor.

The investigator (or designee) will instruct the subject that all dispensed bottles must be returned at each follow-up visit, at which time a capsule/tablet count will be conducted to assure subject dosing compliance.

Additionally, subjects will be required to keep study drug diaries in which they will record the date and time of study drug administrations. These diaries will be dispensed and/or reviewed/collected at each visit.

14.8. Study Drug Storage

All supplies of study drug are to be stored at USP controlled room temperature of 20–25°C (66–77°F) with excursions permitted between 15°C and 30°C (59°F and 86°F). At the clinic, the study drugs are to be stored in a securely locked area, accessible to authorized persons only, until needed for dosing.

14.9. Study Drug Accountability

The US Food and Drug Administration (FDA) and other regulatory agencies require accounting for the disposition of all investigational drugs received by each clinical site. Information on drug disposition required by law consists of the date received, date administered, quantity administered, and the subject to whom the drug was administered. The principal investigator is responsible for the accounting for all unused study drugs and all used study drug containers. The investigator must maintain a complete and current dispensing and inventory record that has been supplied by the sponsor.

14.10. Study Drug Handling and Disposal

At the termination of the study, a final drug accountability review and reconciliation must be completed and any discrepancies must be investigated and their resolution documented.

14.10.1 Disposition of Used Supplies

At the completion of a subject's participation in the trial, all partially used and empty study drug containers must be returned to the investigator (or designee) so that a final subject-dosing inventory may be conducted. This information will be recorded on the Drug Dispensing Log.

14.10.2 Inventory of Unused Supplies

Periodically throughout and at the conclusion of the study, an inventory of unused study drug will be conducted by a representative of the sponsor.

15. CONCOMITANT MEDICATION AND TREATMENT

If the subject must use a concomitant medication during the study, it is the responsibility of the principal investigator to ensure that details regarding the medication are recorded on the eCRF.

A reasonable effort is to be made to document any medications the subject received at the time of signing the ICF through the end of the study (follow-up visit). After discontinuation of study drug, any concomitant medication used during the study in response to an AE is to be recorded on the appropriate eCRF.

Subjects must be receiving glucocorticoid therapy for cGVHD at study entry (subjects also may be receiving CNI therapy). Any changes in corticosteroid, CNI, or ECP doses will be documented.

Use of drugs that prolong QT/QTc should be used with caution in subjects who are receiving KD025. Discuss with medical monitor the appropriate monitoring of subjects while receiving any of these drugs in conjunction with KD025.

The concomitant medication names will be coded by the sponsor according to the World Health Organization Drug Dictionary (WHO-DD) and classified by anatomical therapeutic chemical categories.

The use of medications that are strong CYP3A4 inducers is prohibited. Other CYP3A4 inhibitors / inducers should be used with caution. (See [Appendix H](#) for a listing of these drugs.) CYP1A2 inhibitors/ inducers should be used with caution.

16. SAFETY

16.1. Safety Parameters

The CTCAE v.4.03 will be used for grading toxicities. Laboratory results also will be classified using the CTCAE v4.03. Subjects will be monitored throughout the treatment and follow-up period for occurrence of AEs (acute, delayed, and/or cumulative), as well as for changes in clinical status, vital sign measurements, and laboratory data. Safety parameters to be measured/assessed include vital sign measurements, PE findings, hematology, serum chemistries, and urinalysis results, and ECG recordings.

16.2. Adverse Event Definition

An AE is defined as any untoward medical occurrence in a clinical trial subject associated with the use of a drug, whether or not considered drug related. An AE can be an unfavorable and unintended sign (eg, an abnormal laboratory value finding), a symptom, or a disease temporally associated with the use of a drug, without judgment as to causality. An AE can arise from use of the drug (eg, use in combination with another drug) and from any route of administration, formulation or dose, including an overdose. An AE also includes, but is not limited to, any clinically significant worsening of a pre-existing condition. Examples include:

- Any sign, symptom, physical finding, or laboratory result that has worsened in nature, severity or frequency compared to baseline;
- Reactions from an investigational drug, including those occurring as a result of an overdose, abuse of the study drug, withdrawal phenomena, sensitivity or toxicity;
- Concurrent illness that was not present or worsens in nature, severity, or frequency compared to baseline;
- Injury or accident; and/or
- Exacerbation of a pre-existing condition

For the purpose of data collection, all untoward events that occur after informed consent through 28 days after last dose of study drug are to be recorded on eCRFs by the investigational site.

16.3. Evaluating Adverse Events

The investigator will determine the seriousness, intensity, and causality of an AE associated with the use of the study drug (ie, events where there is a reasonable possibility that the event may have been caused by the study drug) based on the definitions that follow.

16.3.1 Serious Adverse Events

(Notify sponsor or designee within 24 hours)

The SAE definition and reporting requirements are in accordance with Title 21 Part Code of Federal Regulations (CFR) 312.32 and the Guidance for Industry and Investigators Safety Reporting Requirements for Investigational New Drug (INDs) and Bioavailability/Bioequivalence Studies.

SAE: An adverse event is considered "serious" if, in the view of either the investigator or sponsor, it results in any of the following outcomes:

- **Death:** This includes any death that occurs while the subject is “on study” as well as any death that occurs within 28 days after study drug discontinuation.
 - Note:* Death is an outcome of an AE, and not an AE in itself. The event(s) that caused death (eg, illness, accident) is the SAE. Death due to any other cause(s) must also be reported as an outcome of the reportable SAE.
- **Life-threatening AE:** An AE or suspected adverse reaction is considered “life-threatening” if, in the view of either the investigator or sponsor, its occurrence places the patient or subject at immediate risk of death. It does not include an AE or suspected adverse reaction that, had it occurred in a more severe form, might have caused death.
- **Inpatient hospitalization or prolongation of existing hospitalization:** In the absence of an AE, the investigator should not report hospitalization or prolongation of hospitalization. This is the case in the following situations:
 - Hospitalization or prolongation of hospitalization is needed for a procedure required by the protocol
 - Hospitalization or prolongation of hospitalization is part of routine procedure followed by study center
 - Hospitalization for survey visits or annual physicals

In addition, a hospitalization planned before the start of the study for a pre-existing condition which has not worsened does not count as an SAE.

- **Persistent or significant incapacity or substantial disruption of the ability to conduct normal life functions**
- **Congenital anomaly/birth defect**
- **Important medical event:** An event that may not result in death, be life threatening, or require hospitalization may be considered serious when, based upon appropriate medical judgment, it may jeopardize the subject and may require medical or surgical intervention to prevent one of the outcomes listed in this definition.

16.3.2 Suspected Unexpected Serious Adverse Reaction (SUSAR)

(Notify sponsor or designee within 24 hours of first awareness)

A suspected unexpected serious adverse reaction is any adverse drug event, the specificity or severity of which is not consistent with those noted in the current protocol and/or IB. This refers to any AE that has not been previously observed (eg, included in the IB), rather than from the perspective of such an event not being anticipated from the pharmacological properties of the product.

16.3.3 Unexpected Adverse Events

(Notify sponsor or designee by the next business day)

An AE is considered “unexpected” if it is not listed in the IB or is not listed at the specificity or severity that has been observed; or, if an IB is not required or available, is not consistent with the risk information described in the General Investigational Plan or elsewhere in the current application. Also refers to AEs that are mentioned in the IB as occurring with a class of drugs or as anticipated from the pharmacological properties of the drug, but are not specifically mentioned as occurring with the particular drug under investigation.

16.3.4 Non-Serious Adverse Events

All other AEs, not fulfilling the previous definitions, are classified as nonserious.

16.3.5 Protocol-Related Adverse Events

AEs that are not study drug related may nevertheless be considered by the investigator or the medical monitor to be related to the conduct of the clinical study. That is, the event may be

related to the fact that a subject is participating in the study. For example, a protocol-related AE may be an event that occurs during a washout period or that is related to a procedure required by the protocol.

16.3.6 Relationship to Study Drug

The investigator will attempt to assess the relationship of the event to study drug using a 5-point scale (not related, unlikely-related, possibly related, probably related, or definitely related; (see [Appendix G](#)).

16.3.7 Recording Adverse Events

All AEs (including SAEs) are to be accurately recorded on the Adverse Event page of the subject's eCRF during the subject's participation in the study. The severity of each AE will be graded using the CTCAE v 4.03 scale. The date of onset as well as the end date of the event also should be recorded or the event should be entered as "ongoing". In addition, the method used to treat the AE and the outcome of the AE also will be noted. In the event that the grade of an AE worsens, an end date should be entered to the initial AE and a new AE entered with the updated grade and date of onset. The investigator will assess the relationship of the event to study drug. Note: All SAEs also are to be entered onto an SAE form and sent to sponsor or designee.

16.3.8 Hospitalization

In the absence of an AE, the investigator should not report hospitalization or prolongation of hospitalization. This is the case in the following situations:

- Hospitalization or prolongation of hospitalization is needed for a procedure required by the protocol.
- Hospitalization or prolongation of hospitalization is part of routine procedure followed by study center.
- Hospitalization for survey visits or annual physicals.

In addition, a hospitalization planned before the start of the study for a pre-existing condition that has not worsened does not count as an SAE.

16.3.9 Serious Adverse Event Reporting

16.3.9.1. Governing Regulatory Requirements

Compliance with this request for prompt reporting is essential in that the sponsor is responsible for informing the US FDA as well as all other participating investigators of the event.

Under FDA ruling (US Code of Federal Regulations, Title 21 CFR Part 312.32) and the Guidance for Industry and Investigators Safety Reporting Requirements for INDs and BA/BE Studies, the sponsor is required to submit written documentation, in the form of an IND safety report, detailing:

- Any event associated with the use of the drug, that is both serious and unexpected, or
- Any findings from clinical, epidemiological, or pooled analysis of multiple studies or any findings from animal or in vitro testing that suggest a significant risk in humans exposed to the drug.

Written submission must be made by the sponsor to the FDA and the IRB/IECs as soon as possible and in no event later than 15 calendar days after the sponsor's initial notification of the event. Any unexpected death or life-threatening suspected adverse drug reaction must be reported to FDA no later than 7 calendar days after the sponsor's initial receipt of the information. The sponsor shall also inform all investigators.

[figure not shown]
16.3.9.2. Time-Frame for Reporting

Any death, SAE, pregnancy (including pregnancy of a partner), or unexpected (and severe) AE experienced by a subject while receiving or within 28 days of receiving study drug, regardless of relationship to study drug, or any death that occurs more than 28 days after receiving study drug, and is believed to be study drug-related, must be promptly reported (within 24 hours of the investigator becoming aware of the event) by e-mail to the sponsor (or designee).

Contact information for **SAE/SUSAR** reporting:

APCER Life Sciences, Inc.
[contact]
Email: [contact]

Additionally, the investigator will be able to contact the **medical monitor** at all times:

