7.2. Inclusion Criteria

The inclusion criteria are detailed below:

1. Adult male and female subjects at least 18 years of age who have had allogenic bone marrow transplant or hematopoietic stem cell transplantation.
2. Receiving glucocorticoid therapy and calcineurin therapy or glucocorticoid therapy alone for cGVHD at study entry. Subjects on calcineurin therapy only, without glucocorticoid therapy, are not eligible. Subjects also receiving other therapies thought not to be immunosuppressive (such as extracorporeal photopheresis [ECP]), will be considered for enrollment in this study on a case-by-case basis.
3. Have persistent active cGVHD manifestations, as defined by 2014 NIH Consensus Development Project on Criteria for Clinical trials in cGVHD, after at least 2 months of steroid therapy.
4. No more than 3 prior lines of treatment for cGVHD.
5. Karnofsky Performance Scale of > 40 (see [Appendix E](#)).
6. Adequate organ and bone marrow functions evaluated during the 14 days prior to enrollment as follows:
 - a. Absolute neutrophil count $\geq 1.5 \times 10^9/L$ (without myeloid growth factors within 1 week of study entry)
 - b. Platelet count $\geq 50 \times 10^9/L$ (without transfusion or thrombopoietin or thrombopoietin analogues within 2 weeks of study entry)
7. Adequate safety laboratory values:
 - a. Total bilirubin $\leq 1.5 \times$ upper limit of normal (ULN)

- b. ALT and AST $\leq 3 \times$ ULN
 - c. Glomerular filtration rate (GFR) ≥ 30 mL/min/1.73 m² using the 4-Variable Modification of Diet in Renal Disease (MDRD-4) variable formula (see [Appendix F](#))
8. Female subjects of childbearing potential have a negative pregnancy test at screening. Females of childbearing potential are defined as sexually mature women without prior hysterectomy or who have had any evidence of menses in the past 12 months. However, women who have been amenorrheic for 12 or more months are still considered to be of childbearing potential if the amenorrhea is possibly due to prior chemotherapy, anti-estrogens, or ovarian suppression.
9. Women of childbearing potential (ie, menstruating women) must have a negative urine pregnancy test (positive urine tests are to be confirmed by serum test) documented within the 24-hour period prior to the first dose of study drug.

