10. Sexually active women of childbearing potential enrolled in the study must agree to use 2 forms of accepted methods of contraception during the course of the study and for 3 months after their last dose of study drug. Effective birth control includes:
- a. Intrauterine device plus 1 barrier method;
 - b. Stable doses of hormonal contraception for at least 3 months (eg, oral, injectable, implant, transdermal) plus one barrier method;
 - c. Two barrier methods. Effective barrier methods are male or female condoms, diaphragms, and spermicides (creams or gels that contain a chemical to kill sperm); or
 - d. A vasectomized partner
11. For male subjects who are sexually active and who are partners of premenopausal women: agreement to use 2 forms of contraception as in Criterion #10 above during the treatment period and for at least 3 months after the last dose of study drug.
12. Able to provide written informed consent prior to the performance of any study-specific procedures.

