8.4. Treatment Period

8.4.1 Cycle 1, Day 1 (Baseline)

At the Cycle 1 Day 1 visit, subjects will come to the clinic to have the following procedures completed. (Note that if screening assessments are done within 14 days prior to Cycle 1 Day 1, they do not need to be repeated on Day 1).

- Complete PE, including weight
- Seated vital sign measurements (sitting blood pressure, pulse, respiratory rate, temperature)
- Karnofsky Performance Scale score
- Clinical laboratory tests (hematology and serum chemistry panel)
- Supine 12-Lead ECG (to be obtained 4 hours post-morning dose; to be performed 3 times consecutively within 30 minutes [must have an interval of at least 1–2 minutes between ECGs]; perform ECG immediately prior to blood sample collection, if possible)
- Urine pregnancy test (for women of childbearing potential. Positive results are to be confirmed with serum testing.)
- Pulmonary function tests (including forced expiratory volume in 1 second [FEV₁], forced vital capacity [FVC], diffusing capacity of carbon monoxide [DL_{CO}], total lung capacity [TLC], and residual volume [RV])
- PK sample collection (pre-dose [Time 0], and 1, 2, 3, 4, 5, and 6 hours after dosing [after first dose for subjects in the BID group])
- PD blood sample collection (pre-dose)
- Study drug administration
- Dispense study drug
- Dispense study drug diary
- Physician-Reported Global cGVHD Activity Assessment
- cGVHD Activity Assessment - Patient Self Report

- Lee cGVHD Symptom Scale
- Concomitant medications assessment
- AE assessment

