8.8. Long-Term Follow-Up

Subjects will be contacted approximately every 8 weeks and can be contacted via telephone, email or postal mail to confirm survival status and the initiation of any anti-cancer treatment or any changes in treatment of cGVHD. This can also be confirmed from electronic medical records.

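### Contraception is required for 3 months after the last dose, but pregnancy reporting stops at 28 days, so about two thirds of the protocol's own contraception window has no mandatory reporting

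*Protocol*

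**What the plan says.** **Contraception period.** In Protocol 7.2, criterion 10 binds sexually active women of childbearing potential "during the course of the study and for 3 months after their last dose of study drug". Criterion 11 binds sexually active men with premenopausal partners "during the treatment period and for at least 3 months after the last dose of study drug". The synopsis repeats both.

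**Reporting period.** Section 16.3.9.2 lists, among the events to be notified within 24 hours of the investigator's awareness, "pregnancy (including pregnancy of a partner), or unexpected (and severe) AE experienced by a subject while receiving or within 28 days" of study drug, whatever the causal assessment. The same sentence has a late clause for deaths believed to be drug-related, but none for pregnancy. General event collection ends at the same point: under 16.2, "all untoward events that occur after informed consent through 28 days after last dose of study drug are to be recorded on eCRFs".

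**What happens after the last dose.** The End of Treatment list (8.5) has no pregnancy test. The 28-Day Follow-Up visit (8.6) has one, at 28 ± 7 days, and that visit moves forward if a new therapy starts sooner. After it there are only the long-term contacts (8.8). These are made about every 8 weeks by telephone, email or post, or replaced by a look at medical records, and they serve "to confirm survival status and the initiation of any anti-cancer treatment or any changes in treatment of cGVHD".

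**Before the first dose.** Criterion 8 includes women with long amenorrhoea, who are "still considered to be of childbearing potential if the amenorrhea is possibly due to prior chemotherapy" or certain other causes. Criterion 9 reads "Women of childbearing potential (ie, menstruating women) must have a negative urine pregnancy test" within 24 hours of first dose. Table 1 note e states the same 24-hour rule for women of childbearing potential, without the parenthesis. Section 8.4.1 notes that "if screening assessments are done within 14 days prior to Cycle 1 Day 1, they do not need to be repeated" on Day 1. Table 1 note n says the same, and neither makes an exception for the pregnancy test.

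**The concern.** A contraception requirement implies that the sponsor wants conception avoided throughout that period because of the drug. The protocol never calls those 3 months a risk window, so that is an inference, but it is hard to see another reason for the rule. If the precaution fails in the second or third month, the failure falls inside the period the protocol guards and outside the period it records.

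At stake is a small number of reports, each of them scarce information on an investigational drug. The gap is still live: the Amendment 7 rationale in Section 28 refers to remaining subjects whose end of treatment cannot yet be predicted, and each of them will pass through this period.

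**Working it through.** The plan states no figure for this point, so there is nothing to reproduce. The check compares the passages and works out the length of the gap.

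1. **Inputs.** Contraception after last dose: 3 months (7.2, criteria 10 and 11). Pregnancy reporting after last dose: 28 days (16.3.9.2). Last scheduled test: day 28 ± 7, that is day 21 to 35 (8.6). The documents do not convert 3 months to days. I assume 84 days (3 × 28) as the shortest reading and 92 days as the longest.

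2. **Unreported part of the window** = window − 28.
   - 84 − 28 = 56 days; 56/84 = 66.7%.
   - 90 − 28 = 62 days; 62/90 = 68.9%.
   - 92 − 28 = 64 days; 64/92 = 69.6%.

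3. **Untested part of the window** = window − day of last test. Shortest: 84 − 35 = 49 days. Longest: 92 − 21 = 71 days. It is longer still if the visit is brought forward for a new therapy.

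4. **Do other clauses close the gap?**
   - The Safety Evaluation part of the synopsis asks for later untoward events that are known and judged at least possibly related.
   - Section 16.3.9.3 requires later SAEs judged possibly related. Section 16.3.1 counts a congenital anomaly as serious.
   - Both routes need an untoward or serious event and a relatedness judgement. An uncomplicated pregnancy is neither, and the anomaly route works only if someone learns of the pregnancy.
   - The long-term contacts have no pregnancy item.

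5. **Can the existing contacts carry the question?** Section 8.8 gives no starting point for the 8-week interval. Counted from last dose, contacts fall near days 56 and 112. Counted from a day-28 visit, they fall near 28 + 56 = 84 and 84 + 56 = 140. The first contact may therefore come before the window has closed, while the second comes after it on either count (112 and 140 both exceed 92).

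6. **Pre-dose rules side by side.** Criterion 8 includes some amenorrhoeic women, and criterion 9 equates the same term with menstruating women. Note e follows the wider term. The maximum age of the test is 24 hours under criterion 9 and note e. It is 14 days if the general waiver in note n and 8.4.1 is applied literally.

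**The case against.** **The late months are not exposure.** Section 4.2 gives a half-life of 5 to 6 hours, and the longest mean reported for the multiple-dose study in 4.3 is 9.73 hours. Over 28 days, 28 × 24 = 672 hours, and 672/9.73 is about 69 half-lives. A conception in month 2 or 3 therefore follows clearance of the parent drug. This stands as a limit on wording: the 67% to 70% counts calendar days of the contraception window, not days of exposure, and a reader should not infer that exposed pregnancies are being missed at that rate. It does not remove the mismatch, because the protocol itself chose 3 months.

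**Pregnancies that begin in time stay reportable.** The 24-hour clock in 16.3.9.2 runs from awareness, so a pregnancy that began on drug or within 28 days can fairly be read as reportable when found later. That stands, but nothing scheduled after the 28-day visit would bring it to light.

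**Harmful outcomes have a late route.** They do, subject to a relatedness judgement. Uncomplicated pregnancies do not.

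**The pre-dose conflict.** A reader might infer that a woman with chemotherapy-related amenorrhoea, or one tested 14 days earlier, may start drug without a 24-hour test. The documents do not support that. Note e applies the 24-hour test to women of childbearing potential without the narrower parenthesis. Criterion 9 is an eligibility requirement, and a general permission not to repeat assessments does not clearly override it. Urine tests from Cycle 2 onwards (8.4.3) would usually reveal a missed pregnancy while it is still reportable. The Amendment 7 rationale also says that the last subjects enrolled more than a year earlier. What remains is inconsistent wording.

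**Conclusion.** The mismatch is real. The protocol asks subjects to avoid conception for 3 months after the last dose but requires a pregnancy, the subject's or a partner's, to be reported for only 28 days. With 3 months taken as 84 to 92 days, 56 to 64 days (67% to 70%) of that window have no mandatory pregnancy reporting and no scheduled question or test to prompt it.

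The conclusion rests on that conversion and on reading the contraception rule as a drug-safety precaution. With about 48 subjects, few pregnancies are expected. The sample size, the response rate and every planned analysis are unaffected. The change is worth making because it is cheap and the information is otherwise lost. The pre-dose inconsistencies are secondary: they call for reconciliation of the text and are not evidence that subjects were dosed untested.

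**What to change.** 1. In 16.3.9.2, align the reporting period for pregnancy and partner pregnancy with the contraception period in criteria 10 and 11.
2. In 8.8 and Table 1 note m, add a pregnancy and partner-pregnancy question to the long-term contacts. It should be put directly to the subject at the first contact after the contraception period ends. The start of the 8-week interval is not stated, so the question should be tied to the end of the period and not to a contact number. Review of medical records alone should not satisfy it, since a partner's pregnancy may not appear there.
3. Reconcile criterion 8, criterion 9 and Table 1 note e on who is of childbearing potential, and reconcile the 14-day waiver (note n and 8.4.1) with the 24-hour test in criterion 9 and note e. Which testing rule governs is for the sponsor to decide. With enrolment closed, this mainly makes the document consistent.

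The cost is an amendment to wording, one extra question at contacts already planned and a few more reports to process. No visit or test is added.
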